Blood sample for atezolizumab serum biomarker		X ¹³			X ¹³	X ¹³	X ¹³	X ¹³		
Blood sample for atezolizumab plasma biomarker		X ¹³			X ¹³	X ¹³	X ¹³	X ¹³		
Blood sample for protein lysine acetylation ¹³		X ¹⁴		X ¹⁴						
Tissue sample biopsy for immune correlates (also archival tissue when available)	X ¹⁵					X ¹⁵		X ¹⁵		
Entinostat self-administration		Self-administered weekly starting on C1D1; C1D1 ≤3 business days of								

Procedure	Screening (D -21 to -1)	Combination Therapy						EOT (≤7 days of last study drug dose)	Safety F/U (≤30 days of EOT)	Post- Study F/U ¹
		C1			C2		≥C3			
		D1	D8	D15	D1	D15	Day 1			
Visit Window	-	-	±1D	±1D	±3D	±3D	±3D	±3D	±3D	±5D
enrollment										
Atezolizumab administration ¹⁶		X			X		X			
Blood sample for entinostat pharmacokinetics ¹⁷		X ¹⁷	X ¹⁷	X ¹⁷	X ¹⁷					
Blood sample for atezolizumab pharmacokinetics and anti-therapeutic antibodies ¹⁸		X ¹⁸			X ¹⁸			X ¹⁸		X ¹⁸
Pre-treatment/concomitant medications	X	X	X	X	X	X	X	X	X	
Adverse events	X	X	X	X	X	X	X	X	X	
Study drug compliance assessment		X	X	X	X	X	X	X	X	

¹ After the Safety F/U visit, patients who have not experienced PD are followed (including radiological assessments) q6 weeks (+/- 3 d) through study week 36 and then every 9 weeks (+/- 3 d) thereafter until unequivocal PD. Thereafter, they are contacted q3 months until death or study closure for information on PD, alternate treatments and survival status.

² If the screening complete PE was performed within 7 days before C1D1, then a symptom-directed examination may be performed at enrollment.

³ An ECG is to be performed pre-dose on C3D1 (- 3d) and then every 3 cycles (- 3d) thereafter. An ECG may be repeated anytime, as clinically indicated.

⁴ Also performed if fluid retention occurs

⁵ Performed only if last scan was performed >28 days before C1D1

⁶ Patients will have radiological disease assessments performed every 6 weeks (+/- 3 d) through week 36 (Week 6, 12, 18, etc.) and then q9 weeks (+/- 3 d) hereafter during treatment and for patients who have not yet progressed when discontinuing study treatment, until progression based on this schedule.

- Partial or complete response should be confirmed by a repeat tumor imaging assessment at the earliest 4 weeks after the first indication of response, or at the next scheduled scan if on a 6 week schedule, whichever is clinically indicated.

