- If radiologic imaging demonstrates initial evidence for PD, tumor assessment should be repeated at the earliest of 4 weeks, or preferably on the study schedule of 6 weeks, in order to confirm PD.

⁷ Performed only if radiological progression was not previously observed on study.

⁸ For female patients of child-bearing potential, a required serum pregnancy test is to be performed during screening and a urine test within 3 days before the first study drug dose. Pregnancy testing is to be repeated during the study any time pregnancy is suspected.

⁹ Analytes tested: RBC, WBC with absolute counts of individual cell types, platelet count, HGB and HCT. Screening only also includes: prothrombin time (PT) or international normalized ratio (INR) and activated partial thromboplastin time (aPTT). ¹⁰ Analytes tested: ALT, AST, albumin, alkaline phosphatase, total bilirubin, BUN, calcium, creatinine, sodium, potassium, chloride, bicarbonate, glucose, LDH, phosphorus, total protein and uric acid. Magnesium and TSH at enrollment only, unless clinically indicated.

¹¹ Performed only if screening laboratory tests performed >7 days prior to enrollment; screening laboratory results remain as the baseline entry criteria and abnormalities thereafter are to be noted as, and treated as, adverse events

¹² Samples collected pre-dose; not collected after C3 D1 except at EOT.

¹³ Samples collected pre-dose.

¹⁴ Sample taken before any study drug administration.

¹⁵ Fresh tumor core biopsy during screening from all patients on a mandatory basis; required on C2D15 (+/-3 days) until 20 samples are obtained in the Phase 2, but optional for everyone else; optional for all patients at disease progression and end of study treatment. Archival tissue is collected at screening when available.

¹⁶ The initial dose of atezolizumab will be delivered over 60 (\pm 15) minutes. If tolerated without infusion-associated adverse events, the second infusion may be delivered over 30 (\pm 10) minutes and if well tolerated, all subsequent infusions as well. Vital signs should be determined up to 60 minutes before each infusion as well as during and after infusion if clinically indicated.

¹⁷ C1D1 samples are taken pre-dose and 2-4 h post entinostat dosing; C1D8 and C1D15 taken any time after entinostat dosing; C2D1 taken pre-dose

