9.9 Treatment Duration

The duration of treatment for this study is expected to be 1 year. Patients may remain on study until unequivocal progressive disease, unacceptable toxicity, or another treatment withdrawal criteria is met per Protocol [Section 11](#). Study patients with evidence of radiological progressive disease who meet the criteria set forth in Protocol [Section 10.3.2](#) for “Treatment After Initial Radiological Progression”, should continue treatment and be followed according to irRECIST as described in [section 10.3.2](#). Any questions should be directed to the Medical Monitor.

If a patient permanently discontinues either study drug (entinostat/placebo or atezolizumab), the patient will be taken off study treatment and followed for progressive disease per protocol guidelines, or overall survival should progressive disease have been previously determined on study. Patients will receive standard of care outside the auspices of this study at the Investigator's discretion.

After discontinuation of study treatment, patients will complete an EOT visit within 7 days (+/- 3 days) after the last study drug dose and a Safety F/U visit 30 days (+/- 3 days) thereafter.

After completion of the 30-day Safety F/U visit, patients who have not experienced PD are to continue to undergo radiological assessments every 6 weeks until study week 36, and then every 9 weeks thereafter until progressive disease. The purpose of the post-treatment follow-up is to ascertain the duration of PFS for all patients in the study.

After they experience PD, surviving patients are to be contacted every 3-months for documentation of subsequent therapies and survival until closure of the study or patient death, whichever should occur first.

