10.3 Efficacy Assessments

With the exception of OS, all efficacy endpoints in this trial (including the primary endpoint in Phase 2) are linked to the tumor response assessments and therefore the importance of timely and complete disease assessments in this study cannot be understated. Failure to perform any of the required disease assessments will result in the inability to determine disease status for that time point. Frequent off schedule or incomplete disease assessments have the potential to weaken the conclusion of this clinical trial.

The schedule of tumor burden assessments should be fixed according to the calendar, regardless of treatment interruptions. Tumor burden assessments will be performed until progressive disease as per RECIST 1.1 and irRECIST regardless of the discontinuation of study treatment or the start of a subsequent anticancer therapy. Patients with radiographic progression only, as defined by RECIST 1.1 should continue on study treatment until unequivocal progressive disease is determined as defined by irRECIST, at the discretion of the investigator.

The same method of assessment and the same technique used for study screening (CT scan or MRI) to characterize each lesion must be used at each subsequent post-screening assessment. Post-screening scans and the corresponding overall tumor assessment (according to RECIST and irRECIST) should be done at the next visit after the scans are performed and prior to indicating the subsequent cycle, to rule out progressive disease that would warrant study treatment discontinuation.

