17.4 Appendix 4: Immune-related Response Criteria Derived from RECIST 1.1 (irRECIST)

Increasing clinical experience indicates that traditional response criteria may not be sufficient to fully characterize activity in this new era of targeted therapies and/or biologics. This is particularly true for immunotherapeutic agents such as anti-CTLA-4 and anti-PD1\anti PDL1 which exert the antitumor activity by augmenting activation and proliferation of T cells, thus leading to tumor infiltration by T cells and tumor regression rather than direct cytotoxic effects (Hoos 2010; Hodi 2008). Clinical observations of patients with advanced melanoma treated with ipilimumab, for example, suggested that conventional response assessment criteria such as RECIST and WHO criteria are not sufficient to fully characterize patterns of tumor response to immunotherapy because tumors treated with immunotherapeutic agents may show additional response patterns that are not described in these conventional criteria (Hoos 2010; Nishino 2014).

Furthermore, the conventional tumor assessment criteria (RECIST and WHO criteria) have been reported as not capturing the existence of a subset of patients who have an OS similar to those who have experienced CR or PR but were flagged as PD by WHO criteria (Hoos 2010; Nishino 2012).

On these grounds, a tumor assessment system has been developed that incorporates these delayed or flare-type responses into the RECIST 1.1 criteria (irRECIST; Nishino 2014).

Lesion measurability and baseline selection of lesions:

The RECIST 1.1 definitions for measurable and non-measurable lesions apply. At baseline, all tumor lesions/lymph nodes will be categorized as measurable or non-measurable. For target lesions, a Total Measured Tumor Burden (TMTB) for all target lesions will be calculated and reported as the baseline TMTB (similarly to the Sum of Diameters in RECIST 1.1). The baseline TMTB will be used as reference to further characterize any objective tumor response in the measurable dimension of the disease.

New lesions:

irRECIST do not necessarily score the appearance of new lesions as progressive disease. Also, new lesions should be categorized as measurable or non-measurable (same measurability rules as RECIST 1.1. apply).

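### Table 1-1 and section 10.3 end off-treatment imaging at different points, so irRECIST PFS may be censored at the scan that showed RECIST 1.1 progression

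*Protocol*

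**What the plan says.** The protocol gives two kinds of rule for imaging after treatment stops.

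**Restrictive.** In Table 1-1, footnote 7 governs the imaging row at Safety Follow-up and post-study follow-up: "Performed only if radiological progression was not previously observed on study". Footnote 1 says that after the safety visit "patients who have not experienced PD are followed (including radiological assessments) q6 weeks (+/- 3 d) through study week 36". Footnote 6 extends on-study imaging off treatment only "for patients who have not yet progressed when discontinuing study treatment, until progression based on this schedule". Section 9.9 says "patients who have not experienced PD are to continue to undergo radiological assessments every 6 weeks until study week 36". The synopsis follow-up text and section 6.1 set the same entry condition. None of these conditions says whether progression means RECIST 1.1 or irRECIST, or whether it must be confirmed.

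**Inclusive.** Section 10.3: "Tumor burden assessments will be performed until progressive disease as per RECIST 1.1 and irRECIST regardless of the discontinuation of study treatment". The same sentence extends this to patients who have moved to another anticancer therapy. Section 10.3.1.3 asks sites to keep imaging patients who stop without unequivocal progression.

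**In between.** A bullet under footnote 6 reads: "If radiologic imaging demonstrates initial evidence for PD, tumor assessment should be repeated at the earliest of 4 weeks". Table 10-2 and the end of 10.3.2 make that repeat scan discretionary for clinically unstable patients, who are the ones taken off treatment.

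On the criteria, Appendix 4 states: "irRECIST do not necessarily score the appearance of new lesions as progressive disease". PFS by irRECIST is a secondary endpoint (protocol 4.1, SAP 4.2.2), and SAP 11.1 plans separate tables for it with a treatment comparison.

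**The concern.** A site that follows the schedule table can stop imaging at a RECIST 1.1 progression that is not yet progression by irRECIST. For irRECIST PFS that patient is still event-free, so without a later scan she is censored on the day her disease was judged to be progressing by the other criterion. Her later hazard is unlikely to match that of patients still under follow-up, so the censoring is potentially informative and the irRECIST PFS curve would tend to be too high. Scans that were never taken cannot be recovered at analysis.

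**Working it through.** The plan states no figure on this point to reproduce. The check is a comparison of texts, with one calculation to show that the affected patients can exist.

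**1. The rules side by side, for a patient off treatment with RECIST 1.1 PD but no irPD**

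| Text | Further scans? |
|---|---|
| Table 1-1 footnote 7 | No, radiological progression has been seen |
| Footnotes 1 and 6 (main text), synopsis, 6.1, 9.9 | No, if PD is read as RECIST 1.1; yes, if read as irRECIST |
| Footnote 6 bullet | One repeat scan |
| 10.3.2 and Table 10-2, clinically unstable | Repeat scan optional; if it is done and does not show irPD, regular imaging resumes |
| 10.3 | Yes, until PD by both criteria |
| 10.3.1.3 | Yes, until PD is unequivocal |

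Footnote 7 conflicts with 10.3. It also conflicts with the last row of Table 10-2, which resumes regular imaging in patients whose first radiological progression was not confirmed.

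**2. Can RECIST 1.1 PD occur without irPD at the same scan?**

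Inputs from Appendix 4: post-baseline TMTB is the sum over target lesions plus new measurable lesions. irPD needs a rise of at least 20% and at least 5 mm over nadir, or irPD of non-target or new non-measurable lesions. A new non-nodal lesion is measurable from 10 mm. That a new lesion is PD under RECIST 1.1 is implied by the contrast Appendix 4 draws.

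With targets stable at nadir burden T and one new 10 mm lesion, the relative rise is 10/T. The 5 mm condition is met. The 20% condition fails when 10/T < 0.20, that is when T > 10/0.20 = 50 mm.

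| Nadir TMTB (mm) | Rise | irPD by burden? |
|---|---|---|
| 40 | 10/40 = 25% | Yes |
| 50 | 10/50 = 20% | Yes |
| 60 | 10/60 = 16.7% | No |
| 80 | 10/80 = 12.5% | No |
| 100 | 10/100 = 10% | No |

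So above 50 mm, and provided no non-target or new non-measurable lesion is itself irPD, irPD can be seen only on a later scan.

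**3. How the SAP treats her**

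The SAP gives no censoring rules specific to irRECIST PFS. I assume Table 1 in SAP 6.1 applies.

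- No new therapy, alive: row 6 censors at the last scan, which is the RECIST progression scan if none follows.
- New therapy started: row 4 censors at the last scan before it. This happens even if 10.3 is followed, unless irPD is documented first. What footnote 7 removes here is mainly the later scans that sensitivity analysis 4 in Table 2 needs.
- Death: may still count as an event under rows 1–2, subject to the new-therapy and missed-assessment rules.

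Sensitivity analysis 5 does not repair the gap. It covers loss to follow-up and withdrawal of consent, not imaging ended by the schedule. DOR by irRECIST inherits the same censoring rules (SAP 6.5).

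**The case against.** The strongest reply is that the protocol's default runs the other way. The synopsis, 9.9, 10.3 and 10.3.2 all steer patients with a first radiological progression toward continuing treatment under irRECIST, at the investigator's discretion. Stopping at that scan should therefore be mainly a matter of clinically unstable patients, for whom Table 10-2 already makes the repeat scan optional. Rewording footnote 7 alone would not change that. This stands. It limits the group, and it means Table 10-2 has to be part of the reconciliation.

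A reader might infer that irRECIST progression can never be observed once treatment stops. The documents do not support that. The footnote 6 bullet asks for a repeat scan, 10.3.1.3 asks for continued imaging, Table 10-2 allows a discretionary scan, and a death may count. Nor is every RECIST-only progression by burden missed, because irPD can also come through non-target or new non-measurable lesions at the same scan.

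One point widens the group. Section 10.3.2 speaks of confirmed irPD, while the Appendix 4 definition and the SAP's PFS rules do not mention confirmation. If confirmation is required, anyone who stops at first progression without a later scan is affected.

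**Conclusion.** The contradiction is real and should be resolved. A patient with RECIST 1.1 PD that is not irPD at the same scan, who stops treatment then, may have no further required scan beyond a possible confirmatory one. She would be censored for irRECIST PFS at that scan. The tendency is to overstate irRECIST PFS.

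Its size cannot be computed, because the documents give neither the share of RECIST 1.1 progressions that are not irPD nor the share of those patients who stop at once. A reader might assume 20–40% and one half and apply them to the 60 planned events: 60 × 0.20 × 0.5 = 6 and 60 × 0.40 × 0.5 = 12. Nothing in the documents informs either share. The product also ignores repeat scans, deaths and row 4 censoring, so it should not be read as an estimate.

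Two further inferences are not supported. Primary PFS by RECIST 1.1 is not affected, since its event has already occurred. A distorted comparison between arms is not shown either: the trial is double-blind and nothing indicates that the loss would differ by arm.

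The conclusion assumes that at least some sites act on Table 1-1 and that SAP Table 1 governs irRECIST PFS.

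**What to change.** Reword footnotes 1, 6 and 7 of Table 1-1, the synopsis follow-up text, 6.1 and 9.9 to match 10.3. Off-treatment imaging would then continue until PD is documented by both RECIST 1.1 and irRECIST, death, withdrawal or end of study. Changing footnote 7 alone would leave the same restriction in the other places. State whether irPD must be confirmed to end imaging, and reconcile the new text with the Table 10-2 provision for clinically unstable patients; how that provision should read is for the sponsor to settle.

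In the SAP, say explicitly which censoring rules apply to irRECIST PFS. Optionally add a sensitivity analysis that counts patients with RECIST 1.1 PD and no later scan as irRECIST events at that date. It should not be the main rule, because it counts progressions that Appendix 4 may not call irPD and could bias irRECIST PFS downward.

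The cost is a wording amendment and, if adopted, one extra analysis. Sites that would have followed footnote 7 will do some additional off-treatment scans, but none beyond what 10.3 already requires. Patients who start new therapy will still be censored under row 4 in the main analysis; for them the gain is mainly in sensitivity analysis 4.

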2. STUDY GLOSSARY

Abbreviation/Acronym	Definition
ADaM	Analysis Dataset Model
AE	Adverse event
AESI	Adverse Event of Special Interest
ALK	Anaplastic lymphoma kinase
ALP	Alkaline phosphatase
ALT	Alanine aminotransferase
ANC	Absolute neutrophil count
aPTT	Activated partial thromboplastin time
ATA	Anti-tumor activity
aTNBC	Advanced Triple Negative Breast Cancer
AZA	5-Azacitidine
BSA	Body surface area
BUN	Blood urea nitrogen
C	Cycle
CBC	Complete blood count
CBR	Clinical benefit rate
CI	Confidence interval
CIN	Cervical intraepithelial neoplasia
CNS	Central nervous system
CR	Complete response
CrCl	Creatinine clearance
CSC	Cancer stem cell
CT	Computed tomography
CTCAE	Common Terminology Criteria for Adverse Events

Abbreviation/Acronym	Definition
CTLA-4	Cytotoxic T-lymphocyte-associated antigen-4
D	Day
DKA	Diabetic ketoacidosis
DLT	Dose-limiting toxicity
DNA	Deoxyribonucleic acid
DOOR	Duration of response
EC	Ethics Committee
ECG	Electrocardiogram
ECOG	Eastern Cooperative Oncology Group
eCRF	Electronic case report form
EDC	Electronic data capture
EGFR	Epidermal growth factor receptor
EOT	End of Treatment
F/U	Follow-up
FAS	Full Analysis Set
FDG	18F-deoxyglucose
FoxP3	Forkhead box P3
G-CSF	Granulocyte-colony stimulating factor
GFR	Glomerular filtration rate
GI	Gastrointestinal
GM-CSF	Granulocyte macrophage-colony stimulating factor
G-MDSCs	Granulocytic myeloid-derived suppressor cells
HDAC	Histone deacetylase
HIV	Human immunodeficiency virus
IB	Investigator's Brochure

Abbreviation/Acronym	Definition
ICH	International Council for Harmonisation
ID	Identification
IFN- γ	Interferon-gamma
Ig	Immunoglobulin
ILD	Interstitial lung disease
IND	Investigational New Drug Application
INR	International normalized ratio
irAE	Immune-related adverse events
IRB	Institutional Review Board
irRECIST	Immune-related Response Evaluation Criteria in Solid Tumors
ITIM	Immunoreceptor tyrosine-based inhibition motif
ITSM	Immunoreceptor tyrosine-based switch motif
IV	Intravenous(ly)
LDH	Lactic dehydrogenase
mAb	Monoclonal antibody
MDSC	Myeloid-derived suppressor cells
MedDRA	Medical Dictionary for Regulatory Activities
MRI	Magnetic resonance imaging
MTD	Maximum tolerated dose
NCI	National Cancer Institute
NE	Inevaluable
NSCLC	Non-small cell lung cancer
NYHA	New York Heart Association
ORR	Overall response rate
OS	Overall survival

Abbreviation/Acronym	Definition
PD	Progressive disease
PD-1	Programmed death receptor-1
PD-L1	Programmed death ligand-1
PD-L2	Programmed death ligand-2
PET	Positron emission tomography
PFS	Progression-free survival
PK	Pharmacokinetic
PO	By mouth
PP	Per-protocol
PR	Partial response
PT	Prothrombin time
Q2W	Every other week (i.e., every 2 weeks)
Q3W	Every 3 weeks
RBC	Red blood cell (count)
RECIST	Response Evaluation Criteria in Solid Tumors
RP2D	Recommend Phase 2 Dose
SAE	Serious adverse event
SC	Subcutaneous(ly)
SD	Stable Disease
SDTM	Study Data Tabulation Model
SIA	Systemic immune activation
SOC	System organ class
SOD	Sum of Diameters
T1DM	Type 1 diabetes mellitus
T3	Triiodothyronine

Abbreviation/Acronym	Definition
T4	Thyroxine
TEAE	Treatment-emergent adverse event
TGF	Transforming growth factor
TIL	Tumor-infiltrating lymphocyte
TKI	Tyrosine kinase inhibitor
TMTB	Total Measured Tumor Burden
TSH	Thyroid stimulating hormone
TTR	Time to response
ULN	Upper limit of normal
US	United States
V-type	Variable-type
WBC	White blood cell (count)
WoCBP	Women of Child Bearing Potential

3.OBJECTIVES

3.1 Primary

The primary study objectives are:

Phase 1b (Dose Determination Cohort): To determine the dose-limiting toxicities (DLT) and maximum tolerated dose (MTD) or recommended Phase 2 dose (RP2D) of entinostat (SNDX-275) given in combination with atezolizumab.

Phase 2 (Expansion Cohort): To perform an evaluation of the efficacy of entinostat at the RP2D in combination with atezolizumab in patients with aTNBC, as determined by the duration of progression-free survival (PFS) based on the local investigator's assessment of progressive disease using Response Evaluation Criteria in Solid Tumors version 1.1 (RECIST 1.1) .

3.2 Secondary

Secondary study objectives are:

Efficacy: In Phase 2, to evaluate the efficacy of entinostat in combination with atezolizumab in patients with aTNBC, as determined by:

- PFS based on immune-related RECIST (irRECIST)
- Overall response rate (ORR) (i.e., complete response [CR] or partial response [PR]) based on RECIST 1.1 and irRECIST
- Clinical benefit rate (CBR) (i.e. CR or PR or stable disease [SD] for at least 24 weeks) based on RECIST 1.1 and irRECIST
- Overall survival (OS)

In patients with best overall response of CR or PR:

- Duration of response (DOR)
- Time to response (TTR)

Safety: To evaluate safety and tolerability of entinostat in combination with atezolizumab, as measured by clinical adverse events (AEs) and laboratory parameters.

